1. BACKGROUND

Induction of labor (IOL) is the initiation of labor in a viable pregnancy by artificial means, and occurs before the spontaneous onset of labor. A common obstetric intervention, the rate of IOL increased from 9.5% to 22.8% in the US from 1990 to 2012¹. Obese women (BMI \geq 30 kg/m²) are more likely than their normal-weight counterparts to require IOL because of increased rates of obstetric complications including pregnancy related hypertensive disorders, diabetes, and prolonged gestations^{2,3}. Several studies have shown that obese women experience increased labor duration and oxytocin needs when compared to normal-weight women⁴⁻⁸. This in turn results in increased rates for unplanned cesarean delivery (CD) as a result of failed IOL, arrest disorders and non-reassuring fetal heart rate tracing, that is dose-dependent with increasing class of obesity⁹.

Mechanical and pharmacological agents are routinely used for IOL. The supracervical insertion of a Foley balloon catheter acts by overstretching the lower uterine segment and the cervix. This process strips the fetal membranes from the lower uterine segment and causes rupture of the lysosomes in the decidual cells. The lytic enzymes released include phospholipase A, which acts on phospholipids to form arachidonic acid and is converted to prostaglandins¹⁰. Misoprostol (prostaglandin E1, PGE1) is a prostaglandin analogue used to induce labor that is associated with enzymatic collagen degradation, increased water content in the extracellular matrix and stimulation of the myometrium resulting in intrauterine contractions¹⁰. Both methods are supported and recommended by the American College of Obstetricians and Gynecologists (ACOG) due to their high safety profile and comparative effectiveness¹¹. In addition, they are often preferred over oxytocin alone, PGE2 tablet, gel and insert given their low cost, availability and ease of use.

A number of randomized trials have compared the use of the Foley balloon in combination with misoprostol, against misoprostol alone for labor induction (Table 1). Carbone et.al.¹² randomized 123 women undergoing IOL with singleton pregnancies at \geq 24 weeks' gestation with unfavorable cervix (Bishop score \leq 6) to Foley balloon plus vaginal misoprostol or vaginal misoprostol alone. The mean induction-to-delivery time was shorter with the combined approach when compared to vaginal misoprostol alone (15.3 ± 6.5 compared with 18.3 ± 8.7 hours, difference -3.1 hours, 95% CI -5.9 to -0.30). No differences were noted in labor complications, CD rates (37.3 vs 26.2 %, P = 0.90) or neonatal outcomes, likely due to small sample size. These findings contrast with the results by Kashanian et.al.¹³ and Lanka et.al.¹⁴, who did not find such an association. However, the results from Kashanian et.al. must be interpreted with caution given potential biases due to unclear random sequence generation, high allocation concealment and selective reporting. In a recent meta-analysis of eight studies and 1153 patients by Chen et.al.¹⁵, the use of Foley balloon plus misoprostol was associated with a significant reduction in the mean time to delivery when compared to misoprostol alone (mean difference -2.36 hours, 95% CI -4.07 to -0.66; P = 0.007). Differences in cesarean delivery rates, however, remain elusive likely due to the small sample sizes of the trials included.

To our knowledge no studies have compared the effects of these interventions in

women with obesity (BMI ≥ 30 kg/m²). The exact mechanism of failed cervical ripening and dysfunctional labor patterns in obese women is not completely understood. Elevated cholesterol levels have been shown to decrease uterine contractility, and obese women are more likely to have elevated cholesterol levels than are normal-weight women¹⁶. In addition, obesity has been associated with lower prostaglandin sensitivity when used locally for cervical ripening⁸. This association is directly proportional to obesity class. Although many reviews list obesity as a risk factor for failed IOL, this risk has yet to be quantified by obesity class in relation to the various methods available for cervical ripening. In a large study of 1273 women who underwent IOL with vaginal misoprostol, obese women had a longer induction-to-delivery interval (median 22.7, 24.9 and 27.0 hours for normal weight, BMI between 30-39.9 kg/m² and BMI ≥ 40 kg/m², respectively; P < 0.01) and higher CD rates (21.3%, 29.8% and 36.5% for normal weight, BMI between 30-39.9 kg/m² and BMI ≥ 40 kg/m², respectively; aOR 2.32, 95% CI 1.58-3.42). These results were adjusted for parity, race and treatment group. Noteworthy, obese women were more likely to require a CD during the first stage of labor when compared to normal-weight women (74% and 83% vs 62%, respectively). These results were further confirmed by Wolfe et.al.⁹ in a large cohort of 80,887 women from the Ohio Department of Health's Birth Certificate Database. Indeed, pregnant women with class III obesity had a 2.89 aOR of failed IOL rates when compared to normal-weight women. These authors concur that more research is required to define the best method of cervical ripening that would decrease CD rates in this high risk populations.

The combination of Foley balloon plus vaginal misoprostol has not been prospectively compared to the use of vaginal misoprostol alone among women with BMI ≥ 30 kg/m². We hypothesize that obese pregnant women and unfavorable cervix (Bishop score ≤ 6), IOL ≥ 32 weeks gestation using the Foley balloon plus vaginal misoprostol will result in reduced cesarean delivery rates when compared to vaginal misoprostol alone. To prove this hypothesis, we propose a comparative-effectiveness, open-label, randomized controlled trial of induction of labor with transcervical foley balloon and vaginal misoprostol versus misoprostol alone for cervical ripening in obese pregnant women and a Bishop score ≤ 6 .

Table 1. Studies on Foley balloon and vaginal misoprostol for labor induction

| | Foley catheter and duration | Dose of misoprostol | Mean induction-to delivery interval \pm SD (h) in combination group | Mean induction-to delivery interval \pm SD (h) in misoprostol group | Rate of cesarean delivery in combination group | Rate of cesarean delivery in misoprostol group |
|---|--------------------------------------|--|---|---|--|--|
| Rust et al. 2001¹⁷ (n = 81) | 24-Fr 50 mL for 12 h | 25- μ g 3-hourly for 12 h | 16.38 \pm 7.8 | 17.65 \pm 8.6 | 29.7% | 27.5% |
| Chung et al. 2003¹⁸ (n = 146) | 16-Fr 30 mL for 12 h | 25- μ g 3-hourly, 6 doses | 16.6 \pm 8.2 | 17.5 \pm 9.3 | 41.2% | 36.7% |
| Kashanian et al. 2005¹³ (n = 300) | 16-Fr traction with 500 mL serum bag | 25- μ g 3-hourly, 6 doses | 11.7 \pm 2.5 | 10.5 \pm 3 | 35.0% | 40.0% |
| Carbone et al. 2013¹² (n = 123) | 60-mL balloon | 25- μ g 4-hourly till Bishop score $>$ 6 | 15.3 \pm 6.5 | 18.3 \pm 8.7 | 27.3% | 26.2% |
| Lanka et.al. 2014¹⁴ (n = 126) | 16-Fr 30 mL for 12 h | 25- μ g 4-hourly, 8 doses | 26.52 \pm 15.24 | 27.64 \pm 15.63 | 35.0% | 35.0% |

2. METHODS

2.1. Study Objectives

2.1.1. Objective

To compare the CD rate when transcervical Foley balloon plus misoprostol versus vaginal misoprostol alone is used for cervical ripening among nulliparous obese women ($\text{BMI} \geq 30 \text{ kg/m}^2$) and unfavorable cervix (Bishop score ≤ 6).

2.1.2. Rationale

Obese pregnant women are less sensitive to local use of prostaglandins for cervical ripening. Although the best agent and method for IOL remains uncertain among obese women, it is biologically plausible that a combination of a mechanical device (Foley balloon) and a local pharmacological agent (misoprostol) may have an additive or synergistic effect, resulting in a greater degree of cervical ripening, shorter induction-to-delivery time and reduced need for CD due to dystocic labor patterns. The addition of misoprostol to the Foley balloon may also overcome the frequent observation of cervical dilation with the Foley balloon without significant effacement.

2.1.3. Primary Outcome Measures

- Cesarean delivery rate

2.1.4. Secondary Outcome Measures: Maternal

- Indication for CD
- Induction-to-delivery interval (hours)
- Need for oxytocin augmentation
- Occurrence of tachysystole (≥ 5 contractions in a 10 minute period averaged over a 30-minute window) requiring terbutaline or Pitocin cessation.
- Clinical chorioamnionitis: maternal fever $\geq 100.4\text{F}$, uterine fundal tenderness, maternal or fetal tachycardia ($>100/\text{min}$ and $>160/\text{min}$, respectively) and purulent or foul amniotic fluid¹⁹
- Need for operative vaginal delivery
- Composite of maternal morbidity:
 - Maternal ICU admission
 - Postpartum endometritis
 - Surgical-site infections prior to discharge
 - Venous thromboembolism
 - Need for transfusion
 - Maternal death

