2.7. Intervention and Procedures

[figure not shown]
Nulliparous pregnant women at ≥ 32 weeks' gestation admitted to labor and delivery for IOL and who meet the inclusion and exclusion criteria will be approached by the research staff (Figure 1). Group 1 will be composed of women allocated to the Foley balloon plus misoprostol. These women will receive vaginal misoprostol per standard protocol at 25 micrograms every 4 hours. In addition, a 26 Fr-Foley balloon catheter will be inserted by routine clinical standards. The Foley will be inserted through the internal cervical os, filled with 60 mL of normal saline, and then pulled snugly against the internal os. The catheter of the Foley will be taped to the patient's inner thigh under gentle traction. If the Foley is unable to be placed, the patient will be reexamined in 1 hour and placement will be reattempted if Bishop's score is still 6 or less by the healthcare provider. When the Foley balloon had fallen out or had to be removed because 12 hours have passed since insertion as per protocol, further management of labor will be left at the discretion of the labor team.

Group 2 will be composed of women allocated to vaginal misoprostol-only. These women will receive 25 micrograms of misoprostol per vagina every 4 hours. This time interval has been shown to be more effective than different time intervals in a Cochrane review²⁰. Once the cervix becomes favorable (Bishop score > 6), misoprostol administration will be discontinued. Similarly, further management will be left at the discretion of the labor team.

In both groups, if IV oxytocin is indicated, it will be withheld until 4 hours after the last dose of misoprostol to prevent uterine hyperstimulation. Other aspects of labor management will be similar for both groups, including continuous electronic fetal monitoring with external Doppler device or fetal scalp electrode. Uterine contraction assessment will be performed with either an external tocodynamometer or an intrauterine pressure catheter.

Participant data including demographic characteristics, medical and obstetric history, labor course and outcomes will be collected by a dedicated research nurse.

Figure 1. Flow Diagram – CROWN Trial

[figure not shown]

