2.8. Safety Assessment

2.8.1 Risks Associated with Vaginal Misoprostol of Foley Balloon for Labor Induction

[figure not shown]
There is biologic plausibility that a Foley balloon catheter for cervical ripening may be associated with an increased rate of chorioamnionitis because it represents a foreign body in the lower uterine segment and could potentially facilitate an ascending infection. However, a systematic review by Fox et.al.²¹ (Figure 2) and a Cochrane review from Jozwiak et.al.^{22,23} (Figure 3) concluded that the rates of chorioamnionitis were comparable for the Foley balloon and misoprostol when used independently. Carbone et. al.¹² also reported no differences in the rates of chorioamnionitis when the Foley balloon was used concomitantly with misoprostol versus misoprostol alone.

Figure 2. Impact of Misoprostol vs Foley Balloon on Risk of Chorioamnionitis

Adapted from Fox NS, Saltzman DH, Roman AS, Klausner CK, Moshier E, Rebarber A. Intravaginal misoprostol versus Foley catheter for labour induction: a meta-analysis. *BJOG Int J Obstet Gynaecol* 2011;118:647–54.
 Abbreviations: CI, confidence interval; LCI, lower confidence interval; UCI, upper confidence interval

Figure 3. Impact of Prostaglandins vs Balloon catheter on Risk of Chorioamnionitis

Adapted from Jozwiak M, Bloemenkamp KWM, Kelly AJ, Mol BWJ, Irion O, Bouvain M. Mechanical methods for induction of labour. *Cochrane Database Syst Rev* 2012;3:CD001233.
 Abbreviations: CI, confidence interval

Tachysystole is a common complication of misoprostol administration for cervical ripening, and tachysystole with FHRT changes is more frequent among women receiving misoprostol than among those treated with mechanical devices, alternate prostaglandin compounds or oxytocin^{20,24,25}. However, the frequency of uterine tachysystole with FHRT changes was lower when a Foley balloon catheter was added to misoprostol than when misoprostol alone was used^{22,26}, purportedly due to the reduced need for additional doses of vaginal misoprostol. The combination could provide extra benefits to patients who are at higher risk of fetal hypoxemia, such as those with sickle cell disease, oligohydramnios, fetal growth restriction or other chronic diseases for which the use of misoprostol is not considered contraindicated^{27,28}.

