2.9. Statistical Considerations

2.9.1. Sample Size

Assuming a cesarean delivery rate of 53% at Memorial Herman Hospital among nulliparous obese women who underwent IOL in 2012 at ≥ 32 weeks and met our inclusion criteria, 250 women (125 women per group) would be required for 80% power to detect a 33% cesarean delivery rate reduction between the 2 groups using a two-tailed t test and α of 0.05 (Table 2). Interim analysis after 50% enrollment will be performed in order to determine if the risk of adverse events discussed in the secondary outcomes is increased in one arm relative to the other arm.

Table 2. Proposed Sample Size

| % decrease in CD rate | Power (%) | | |
|-----------------------|-----------|-----|-----|
| | 80 | 85 | 90 |
| 33 | 250 | 270 | 316 |
| 40 | 172 | 196 | 228 |

| | | | |
|----|-----|-----|-----|
| 50 | 100 | 114 | 134 |
|----|-----|-----|-----|

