2.9.2. Statistical Tests

An intent-to-treat analysis will be conducted. Selected baseline characteristics and outcome measures will be compared using the independent t test for continuous variables and the X^2 or Fisher's exact test for categorical variables as appropriate. Mann-Whitney U test will be used for non-parametric comparisons. Tests with a p-value < 0.05 will be considered significant.

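### Does the missing denominator for the indication for cesarean make that secondary outcome misleading?

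*Combined protocol and SAP*

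**What the plan says.** Section 2.1.4 (maternal secondary outcomes) gives the item as "Indication for CD" and nothing more. It does not list the indications, define them, or say what value a woman who delivers vaginally takes.

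Section 2.9.2 is the only text on analysis. It states "An intent-to-treat analysis will be conducted" and sends categorical measures to a chi-square test or to Fisher's "exact test for categorical variables as appropriate". It speaks of selected baseline characteristics and outcome measures, without saying which outcomes will be tested or in which women.

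Three other places bear on the point. Section 1 names the reasons for unplanned cesarean in obese women: "failed IOL, arrest disorders and non-reassuring fetal heart rate tracing". Section 2.1.2 expects a benefit through "reduced need for CD due to dystocic labor patterns". Section 2.7 says that "labor course and outcomes will be collected by a dedicated research nurse", so the reason for each cesarean should be on file.

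**The concern.** An indication exists only for a woman who had a cesarean. An analyst applying section 2.9.2 mechanically could cross-tabulate indication by arm among cesareans and run a chi-square test. Having a cesarean is the primary outcome, so the two groups in that table would be formed after randomisation by the event the treatment is meant to change.

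The possible distortion is easy to see. Section 2.1.2 places the expected benefit in dystocia. If dystocia cesareans fall more than the rest, the remaining indications take up a larger share of a smaller total. A significant test on that share could be read as more cesareans for fetal or other reasons with the Foley, when the risk per randomised woman is the same or lower. This is the only listed outcome that separates cesareans by cause, so a misreading would bear on the trial's account of how the intervention works.

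**Working it through.** **Inputs from the plan (section 2.9.1).** Control cesarean rate 53% ("Assuming a cesarean delivery rate of 53"%); relative reduction 33%; 125 women per arm; 80% power; two-sided α of 0.05. The combination-arm rate is 0.53 × 0.67 = 0.3551.

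**Input not in the plan.** The indication mix. I assume that 80, 70 or 60% of control cesareans are for dystocia, so 20, 30 or 40% are for other reasons. The relative fall in other-indication cesareans is also a scenario value: 0, 10, 20 or 33%.

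**1. The plan's own figure.** With pooled variance and no continuity correction,

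n per arm = [1.96·√(2·p̄·(1−p̄)) + 0.8416·√(p₁(1−p₁) + p₂(1−p₂))]² / (p₁−p₂)², where p̄ = 0.44255.

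This is (1.3768 + 0.5819)² / 0.1749² = 125.4, so 126 per arm and 252 in total against the stated 250. Power at 125 per arm is 79.9%. The planning rates are sound to work from.

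**2. Size of a cesarean-only table.** 125 × 0.53 = 66.25 and 125 × 0.3551 = 44.39, so about 66 against 44 women.

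**3. Worked case: 70% dystocia, only dystocia falls.** Other-indication risk is 0.30 × 0.53 = 0.159 of women in both arms.

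| | Misoprostol | Foley + misoprostol |
|---|---|---|
| Other-indication CD, share of all women | 15.9% | 15.9% |
| Dystocia CD, share of all women | 37.1% | 19.6% |
| Other-indication CD, share of cesareans | 0.159/0.53 = 30% | 0.159/0.3551 = 45% |

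For the last row, the pooled share is 39.75/110.64 = 0.359. The standard error is √(0.359 × 0.641 × (1/66.25 + 1/44.39)) = 0.093, and z = 0.148/0.093 = 1.59. The chance of exceeding 1.96 is about 36%.

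**4. Range over scenarios.** 200,000 simulated trials per scenario, three outcomes per woman (dystocia CD, other CD, no CD), uncorrected chi-square among cesareans. Rejection rates:

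| Relative fall in other-indication CD | Dystocia share 80% | 70% | 60% |
|---|---|---|---|
| 0% (only dystocia falls) | 23% | 36% | 53% |
| 10% | 14% | 20% | 30% |
| 20% | 8% | 10% | 13% |
| 33% (proportional) | 5% | 5% | 5% |

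In the 10% and 20% rows, at least 91% of rejections show a higher share of other indications with the combination, although their true risk per woman is lower.

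**5. Keeping no cesarean as a third category.** A single 2-df test on all women rejects in about 71% of trials when the mix is unchanged (proportional fall). It mostly picks up the primary effect and says little about cause.

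**6. Each indication counted in all randomised women.** Other-indication cesarean is tested at about 5% when its risk is unchanged. Dystocia cesarean has 84 to 91% power if only dystocia falls, and 47 to 65% under a proportional fall. In the worked case the 95% CI half-widths are 1.96·√(2 × 0.159 × 0.841/125) = 9.1 points for other indications and 1.96·√((0.371 × 0.629 + 0.196 × 0.804)/125) = 11.0 points for dystocia.

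**7. What the text commits to.** No sentence names cesareans as the analysis set. The one sentence on population is the intent-to-treat statement. Taken with indication counts by arm, it leads to step 6: divide each count by 125.

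**The case for a change.** The case for a change is that the intent-to-treat statement does not define an indication for a woman without a cesarean, so it cannot fix the denominator by itself. The cesarean-only test is then the easy default, and section 2.1.2 predicts the uneven fall that makes it mislead. Two or three lines of text would remove the doubt, with no new data.

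Part of this stands. The denominator is not stated, the arithmetic is right, and a per-woman count is the better summary. Three things weaken the rest.

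- **The harm needs an analysis the plan does not prescribe.** The largest rates also need the whole benefit to sit in dystocia. Section 2.1.2 names that mechanism but does not call it the only one. Section 2.8.1 reports that the "frequency of uterine tachysystole with FHRT changes was lower when a Foley balloon catheter was added to misoprostol", which makes some fall in tracing-related cesareans plausible and moves the result towards the lower rows of the table.
- **The rejections are not false positives.** Wherever the fall is uneven, the mix among cesareans really does differ between arms. The error comes only if a reader takes a share of cesareans for a risk per woman, and counts shown beside the arm totals let the reader see the difference.
- **A recode would gain little.** Indications compete, since a woman delivered for dystocia cannot later be delivered for a tracing. The trial is open-label (section 2.2), and labor management after ripening is left to the clinical team (section 2.7), so attribution is partly discretionary. A per-woman yes/no outcome inherits both limits, with intervals of about 7 to 12 points either side.

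**Conclusion.** The observation is correct but calls for no change. The plan leaves the denominator and categories of one secondary outcome unstated. Followed as written, with intent-to-treat and counts by arm, it still gives sound conclusions. An analyst can report each indication out of all randomised women and show the mix among cesareans descriptively, using data already collected.

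If a cesarean-only test were run instead, its rejection rate would lie between 5% and 53% over the scenarios above. That range rests on an assumed dystocia share of 60 to 80% and on assumed falls by indication, neither of which the documents give. The primary comparison of cesarean rates and the sample size of 250 do not depend on the point.

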2.6. Randomization

Randomization will be achieved by computer-generated random sequences. Permuted block randomization will be performed, stratified by center. Women will be randomized to either Foley balloon plus misoprostol or misoprostol alone as the method of choice for IOL. Enrollment number and assignments will be placed in opaque sealed envelopes. Envelopes will be kept secured in a locked office and will be accessible only by the research personnel.

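### Does the induction-to-delivery interval need a written start, a route label and a competing-event analysis beside it?

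*Combined protocol and SAP*

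**What the plan says.** The combined protocol and SAP lists the outcome in section 2.1.4 as "Induction-to-delivery interval (hours", with no start event and no rule for route. Section 2.1.2 names two expected benefits side by side: "shorter induction-to-delivery time and reduced need for CD due to dystocic labor patterns". It does not define the interval either.

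Section 2.9.2 sets the analysis: "An intent-to-treat analysis will be conducted", with a t test for continuous outcomes, and "Mann-Whitney U test will be used for non-parametric comparisons". It gives no time-to-event method and no analysis by route.

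Section 2.7 gives vaginal misoprostol to both groups and adds a Foley balloon in Group 1. It does not state the order of the two. If the balloon cannot be placed, the woman is re-examined after 1 hour, and a second attempt depends on her Bishop score. Figure 1, the flow diagram, is not shown in the text available, so a start marked only there could not be checked.

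**The concern.** Two things look wrong at first.

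**Route.** The sample size section starts from "Assuming a cesarean delivery rate of 53" percent and plans for a 33% relative reduction. Many intervals will therefore end in cesarean, in unequal shares by arm. The Background adds that "obese women were more likely to require a CD during the first stage of labor", so cesarean times may differ from vaginal times. The difference in hours then combines progress to vaginal delivery with how often, and when, labor ends in cesarean. A reader might take it as a statement about induction speed alone.

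**Start.** In Group 1 the clock could be read as starting at misoprostol or at Foley insertion. Under the second reading, a woman in whom the balloon is never placed has no start time, and a delay could enter one arm only. The trial is open label and recruits at three hospitals, so the reading could vary.

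At stake is the interpretation of one secondary outcome.

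**Working it through.** **1. The plan's own figure.** Inputs from section 2.9.1: p1 = 0.53, p2 = 0.53 × 0.67 = 0.3551, two-sided α 0.05, power 80%. With the pooled normal formula,

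n = [1.96·√(2 × 0.44255 × 0.55745) + 0.8416·√(0.53 × 0.47 + 0.3551 × 0.6449)]² / 0.1749² = 125.4,

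so 126 per group and 252 in total, against the stated 250. Power at 125 per group is 79.9%. Expected cesareans are 125 × 0.53 = 66 and 125 × 0.3551 = 44. About 44% of all intervals would end in cesarean.

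**2. Effect of route mix alone.** The documents give no times by route, so the gap is an assumption. If timing within each route is the same in both arms, the shift in the mean (combination minus misoprostol alone) is −0.1749 × (mean cesarean time − mean vaginal time). Gaps of −6, −3, +3, +6 and +9 h give +1.05, +0.52, −0.52, −1.05 and −1.57 h. The cited meta-analysis reports −2.36 h. These shifts are real differences in time to delivery, not artefacts of the test.

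**3. Does the planned test mislead?** Take the 123-woman trial in the Background ("15.3 ± 6.5 compared with 18.3 ± 8.7 hours") and use its misoprostol arm as control: mean 18.3 h, SD 8.7 h, CV 0.475. This gives a Weibull shape of 2.22 and a scale of 20.66 h. Assume proportional cause-specific hazards, with control shares of 0.47 vaginal and 0.53 cesarean. Let H be the total hazard in the combination arm relative to control. Then the mean is 18.3 × H^(−1/2.22), the vaginal hazard ratio is H × 0.6449/0.47, and the cesarean hazard ratio is H × 0.3551/0.53. All three scenarios produce the planned cesarean rates.

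| Scenario | H | Vaginal HR | Cesarean HR | Mean difference | t test rejects |
|---|---|---|---|---|---|
| A: only the cesarean hazard falls | 0.47/0.6449 = 0.729 | 1.00 | 0.49 | +2.8 h | 65% |
| B: only the route mix changes | 1 | 1.37 | 0.67 | 0 h | 5% |
| C: only the vaginal hazard rises | 0.53/0.3551 = 1.493 | 2.05 | 1.00 | −3.0 h | 85% |

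Rejection rates are from simulation with 125 per arm. In A and C the arms truly differ in time to delivery, and rejecting is correct. In B the times are identical, and the test keeps its 5% level.

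**4. Would competing-event tests settle the mechanism?** The cause-specific log-rank tests reject in 5%, 45% and 99% of trials for vaginal delivery, and in 96%, 54% and 5% for cesarean (A, B, C). A and C separate well, but B does not. When B is true, cesarean alone is significant (the pattern of A) in about 31% of trials, vaginal alone (the pattern of C) in 20%, both in 24%, and neither in about 24%. Roughly half of B trials would be read as A or C.

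In a second model, vaginal timing is identical in both arms (mean 17 h, SD 8 h) and cesareans come 8 h or 4 h earlier, at the same time, or 4 h or 8 h later. The vaginal log-rank then favors the combination in 16%, 29%, 45%, 61% and 70% of trials.

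**5. The start.** The standard error of the mean difference is 8.7 × √(2/125) = 1.10 h. The documents give no rate of failed insertion. At an assumed 5% to 20%, a 1-hour wait moves the Group 1 mean by 0.05 to 0.20 h, or 0.05 to 0.18 standard errors. At an assumed 50% it is 0.5 h. Only if every Group 1 woman lost an hour would the shift reach about one standard error (1/1.10 = 0.91).

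**The case for a change.** The best case for a change is that it is cheap. The same outcome list defines tachysystole and chorioamnionitis with thresholds, so the authors did define outcomes where they saw a need. One sentence would fix the start before data are seen. Delivery time and route are collected anyway, so cumulative incidence curves would cost little. As the table shows, the planned cesarean result is compatible with a longer, unchanged or shorter interval, and the interval alone does not say which mechanism is at work.

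Some of this stands. The readable text names no start, and the interval does not separate its components. But it was not asked to. Section 2.1.2 treats a shorter interval and fewer cesareans as two benefits, and nowhere does the plan claim faster progress to vaginal delivery. Route mix will be visible, because the cesarean rate is the primary outcome and indication for cesarean, oxytocin need and operative vaginal delivery are listed beside the interval. Only timing by route is absent.

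The proposed addition overlaps the primary outcome, has modest power (45% at a vaginal hazard ratio of 1.37) and is not a pure measure of speed either.

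On the start, intention to treat requires an interval for every randomized woman. That already argues against successful Foley placement, which some women may never have. The first misoprostol dose has its own weakness: section 2.7 does not fix the order, so if the Foley went in first, a misoprostol clock would omit part of Group 1's induction. A common event such as randomization or the first intervention of either kind is the sensible reading, and an analyst would reach it unaided.

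**Conclusion.** No change to the plan is needed. Read plainly, the outcome is time to delivery by any route in all randomized women, and the planned comparison of it is valid. A route label would only restate that meaning. The unstated start is missing detail with a likely effect of 0.05 to 0.20 h against a standard error of about 1.1 h. A competing-event description is a legitimate optional extra, but it corrects no error and does not reliably identify the mechanism.

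The conclusion rests on assumptions. The failure rate of Foley insertion is assumed. The interval shape is borrowed from a trial with 26.2% cesareans in its misoprostol arm, and the Background gives longer medians for obese women (24.9 and 27.0 h). Across the five misoprostol arms of Table 1, scenario A ranges from 0.9 to 5.2 h longer and C from 1.0 to 5.4 h shorter, so size and sign cannot be fixed from the documents. The validity of the any-route comparison does not depend on them. It would be weakened only if the clock started at different events in the two arms with a delay well beyond the 1-hour wait described, and nothing in the text calls for that.

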2.2. Design Summary

This is a comparative-effectiveness, open-label, randomized controlled trial of induction of labor with transcervical Foley balloon and vaginal misoprostol versus misoprostol alone in nulliparous obese pregnant women and Bishop score ≤ 6 .

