2.8.2. Specification of Safety Parameters

Both of the interventions proposed are done in routine clinical care and have been tested in prior trials. Choriamnionitis is in fact a risk but is comparable to standard of care. The medications/interventions are not new in pregnancy and misoprostol is known to not be teratogenic in the third trimester. Therefore, the establishment of a safety data monitoring board is not necessary. The principal investigator (PI) and mentor will monitor the progress of study and determine the safety parameters.

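### Does the chorioamnionitis definition in section 2.1.4 need a stated count of signs before the arms are compared?

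*Combined protocol and SAP*

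**What the plan says.** Section 2.1.4 of the combined protocol and SAP lists clinical chorioamnionitis among the secondary maternal outcomes. It gives a temperature limit of 100.4 F for fever, then "uterine fundal tenderness, maternal or fetal tachycardia" with limits of 100 and 160 per minute, and ends with "respectively) and purulent or foul amniotic fluid". A citation follows (reference 19). Only its title appears in the document.

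Section 2.8.1 says that "a Foley balloon catheter for cervical ripening may be associated with an increased rate of chorioamnionitis". It then reports that two reviews "concluded that the rates of chorioamnionitis were comparable for the Foley balloon and misoprostol when used independently", and that an earlier randomized trial "reported no differences in the rates of chorioamnionitis when the Foley balloon was used concomitantly with misoprostol versus misoprostol alone".

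Section 2.8.2 states that "Choriamnionitis is in fact a risk but is comparable to standard of care", and goes on to conclude that "the establishment of a safety data monitoring board is not necessary". Section 2.9.1 plans an interim look after half of enrollment, to see whether adverse events among the secondary outcomes are more frequent in one arm. Section 2.9.2 plans an intent-to-treat analysis, with a chi-square or Fisher's exact test for categorical outcomes and significance at p < 0.05.

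**The concern.** A definition made of several signs usually says how many must be present and whether any one is mandatory. This one does not. Under the literal reading, a woman with fever, tenderness and tachycardia but clear fluid is not a case. If the list is only a catalogue of signs, with the counting rule left to the citation, she might be one. The two readings can give different case counts.

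Three features of the trial make the question look more serious. Chorioamnionitis is the harm that the protocol itself links to the balloon. The interim look is the only comparison of safety by arm scheduled before the end, and there is no monitoring board. Section 2.2 also makes the design open: "This is a comparative-effectiveness, open-label, randomized controlled trial of induction of labor". A counting rule left unsettled could in principle be chosen by people who already know the assignments and the data.

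**Working it through.** The plan states no chorioamnionitis rate, so there is no figure of its own to reproduce. The check is mainly one of wording.

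**1. Is there a rule?** Section 2.1.4 has four items. Tachycardia counts once, with maternal and fetal as alternatives. The items are joined by a conjunction, and fever and both tachycardias have numeric limits. No phrase asks for a minimum number or makes one sign mandatory and the others supportive. In ordinary reading all four are required, and a data collector can apply that.

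**2. Does anything contradict it?** Sections 2.8.1 and 2.8.2 discuss the risk, 2.9.1 the interim look and 2.9.2 the tests. None gives another case definition or a count. Reference 19 is present by title only, so the document does not show whether its rule differs from the literal one.

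**3. Could one woman's classification matter?** For illustration, assume Fisher's exact test at p < 0.05 at the interim look, although section 2.9.1 names neither test nor threshold. Half of 250 is 125 women, taken as 63 and 62. With no case in the smaller arm:

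- Six cases: P(all in the arm of 63) = C(63,6)/C(125,6) = 0.0145, and the opposite extreme is C(62,6)/C(125,6) = 0.0131. Two-sided p = 0.0276.
- Five cases: p = 0.0576.

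At 125 per group, 6 v 0 gives p = 0.0294 and 5 v 0 gives 0.0600.

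So one case can move p across 0.05. The crossing depends on the test, however. The uncorrected chi-square for 5/63 v 0/62 is 125 × (5 × 62)² / (63 × 62 × 5 × 120) = 5.13, p = 0.024, which stays below 0.05. It also depends on a 63/62 split, which blocks stratified by center do not guarantee. The same sums hold for any uncommon yes/no outcome, so they say nothing particular about this definition.

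**4. How informative is the comparison?** The rates here are assumptions, since the document gives none. The formula is the two-proportion normal approximation (pooled variance under the null), two-sided α = 0.05, 80% power, 125 per arm.

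| Assumed misoprostol-only rate | Expected cases in 125 | Balloon-arm rate detectable | Ratio |
|---|---|---|---|
| 2% | 2.5 | 10.6% | 5.3 |
| 5% | 6.25 | 15.8% | 3.2 |
| 10% | 12.5 | 23.2% | 2.3 |
| 20% | 25 | 35.9% | 1.8 |

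A stricter rule can only lower the rate, which moves the comparison up this table. Even at 20% the detectable rate is 1.8 times the control rate. The trial was sized for cesarean delivery, and this comparison is coarse under either reading.

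**The case for a change.** The best case for a change is that it costs almost nothing and that timing matters. One sentence in section 2.1.4, written before any comparison by arm, would stop the rule being settled after the data are seen. Recording each sign separately would let the outcome be derived under either reading. If the literal rule is meant, the sponsor would only have to say so.

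Part of this stands. The text does not say outright whether the list is a conjunction or a catalogue, and a confirmation would be tidy. The rest is weaker. The catalogue reading needs a reason to set aside the plain conjunction, and the document supplies none. Section 2.7 assigns collection of labor course and outcomes to a dedicated research nurse. The data form is not part of the document, so the signs may already be recorded separately. Intent-to-treat analysis in section 2.9.2 already settles the denominator. Bedside judgement of tenderness and fluid by unmasked staff, and the absence of a monitoring board, are separate matters that a count of signs would not alter.

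**Conclusion.** No change to the plan is needed. The definition is terse, but it can be applied as written: all four signs, the same in both arms. An analyst would apply that rule, state it in the report, and could show a broader count as a supplement if the signs are recorded separately. The sponsor may confirm the reading in one line as an editorial matter, and the choice of rule is the sponsor's.

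No effect on any result, and no bias between arms, can be derived from the document. The primary outcome and the sample size of 250 are unaffected. This conclusion rests on taking the conjunction at its ordinary meaning and on the absence of any competing definition elsewhere in the text. A statement from the sponsor that a different combination was intended would change the case counts, but would still concern one secondary outcome.
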